11.6.1.4 Clinical Laboratory Evaluations

Descriptive statistics for clinical laboratory values (in SI units) and changes from the baseline values at each assessment time point will be presented by treatment group for each clinical laboratory parameter. The number and percentage of subjects with PCS postbaseline clinical laboratory values will be tabulated by treatment group. The criteria for PCS laboratory values will be detailed in the SAP. The percentages will be calculated relative to the number of subjects with available non-PCS baseline values and at least one postbaseline assessment. The numerator will be the total number of subjects with available non-PCS baseline values and at least one PCS postbaseline value. A supportive listing of subjects with PCS postbaseline values will be provided, including the SID number, study center number, and baseline and postbaseline values. A listing of all AEs for subjects with PCS laboratory values will also be provided.

CONFIDENTIAL

11.6.1.5 Columbia-Suicide Severity Rating Scale

For the C-SSRS, the number and percentage of subjects with suicidal ideation or suicidal behavior as recorded on the C-SSRS scale will be presented by treatment group. The distribution of responses for most severe suicidal ideation and suicidal behavior during the lifetime history, the double-blind treatment period and the down taper period will also be presented by treatment group for the Safety Population. Supportive listings will be provided and will include the SID number, treatment group, visit number, lifetime history, and postbaseline values for each patient. Intensity of ideation, suicidal behavior type, and lethality of suicidal behavior will also be included in these listings.

11.7 Pharmacokinetic and Exposure-Response Evaluation

Escitalopram and S-demethylcitalopram plasma concentrations will be listed.

Escitalopram concentrations will be analyzed using a nonlinear mixed effects approach. Population PK parameters, inter-subject, and residual variability will be determined. The effect of covariates on the escitalopram PK will also be investigated. The exposure/dose-response relationship between efficacy parameters and plasma exposure and potentially safety parameters and plasma exposure will be explored using a nonlinear mixed effects approach. The analysis results will be provided in a separate report.

11.8 Interim Analyses

A blinded interim analysis will be conducted when 75% of randomized subjects have either completed or discontinued the study to obtain an estimate of the pooled standard deviation on change from baseline in the PARS score to Week 8 of the double-blind treatment period. If the estimated pooled standard deviation is larger than the assumed pooled standard deviation in the sample size calculation due to assumption deviation as well as COVID-19 remote visits (see [Section 11.9](#)), sample sizes in placebo and escitalopram treatment groups may be increased to ensure an adequate power. However, due to the difficulties in recruiting pediatric subjects with GAD, the number of subjects in each treatment arm will be capped at 160.

11.9 Determination of Sample Size

The sample size estimate was constructed using a simulation approach as described in Lu K. (2012)¹⁸.

The primary efficacy parameter will be the change from baseline to Week 8 of the double-blind treatment period in PARS total score. To detect an effect size (treatment group difference of 2.30 units relative to pooled standard deviation of 5.79¹⁹) of 0.39, a sample size of 128 subjects in the escitalopram treatment group and 128 subjects in the placebo group will provide 85% power based on an MMRM model using simulation

CONFIDENTIAL

method. The simulation assumed a correlation of 0.7 between the repeated measures, and a common dropout rate of 14%, based on historical data of escitalopram in pediatric subjects.

11.10 Protocol Deviations

Deviations from the protocol will be documented on an ongoing basis based on monitoring reports (eg, failure of eligibility criteria). Protocol deviations may also be identified by data management checks or statistical programming (eg, study treatment compliance, duration of study treatment, study completion, prohibited medications based on drug codes).

12 QUALITY ASSURANCE AND QUALITY CONTROL

12.1 Audit and Inspection

Study centers and study documentation may be subject to Quality Assurance audit during the course of the study by the sponsor or its nominated representative. In addition, inspections may be conducted by regulatory authorities at their discretion.

12.2 Monitoring

Data for each subject will be recorded on an eCRF. Data collection must be completed for each subject who signs an ICF/assent and is administered study drug.

In accordance with cGCP and ICH guidelines, the study monitor will carry out source document verification at regular intervals to ensure that the data collected in the eCRF are accurate and reliable.

The investigator must permit the monitor, the IRB, the sponsor's internal auditors, and representatives from regulatory authorities direct access to all study-related documents and pertinent hospital or medical records for confirmation of data contained within the eCRFs.

12.3 Data Management and Coding

Syneos Health will be responsible for activities associated with the data management of this study. This will include setting up a relevant database and data transfer mechanisms, along with appropriate validation of data and resolution of queries. Data generated within this clinical study will be handled according to the relevant standard operating procedures of the data management and biostatistics departments of Syneos Health.

Study centers will enter data directly into an electronic data capture (EDC) system by completing the eCRF via a secure internet connection. Data entered into the eCRF must be verifiable against source documents at the study center. Data to be recorded directly

CONFIDENTIAL

on the eCRF will be identified and the eCRF will be considered the source document. Any changes to the data entered into the EDC system will be recorded in the audit trail and will be FDA CFR 21 Part 11 compliant.

Medical coding will use MedDRA for concomitant diseases and AEs and WHO Drug for medications.

Missing or inconsistent data will be queried in writing to the investigator for clarification. Subsequent modifications to the database will be documented.

12.4 Quality Management and Risk Evaluation

Details are provided in [Section 8.2.2](#).

CONFIDENTIAL

13 RECORDS AND SUPPLIES

13.1 Drug Accountability

On receipt of the study drug (including rescue medication, if relevant), the investigator (or deputy) will conduct an inventory of the supplies and verify that study drug supplies are received intact and in the correct amounts before completing a supplies receipt. The investigator will retain a copy of this receipt at the study center and maintain the original receipt in the site investigator file. The monitor may check the study supplies at each study center at any time during the study.

It is the responsibility of the study monitor to ensure that the investigator (or deputy) has correctly documented the amount of the study drug received, dispensed, and returned on the dispensing log that will be provided. A full drug accountability log will be maintained at the study center at all times. In addition, sites will be provided a separate Investigational Product Curbside Pickup and Shipment Tracking Form to document pertinent study drug dispensing information each time a new shipment of study drug is shipped directly to a subject's residence, dispensed curbside at the site, or delivered to a subject's residence via site personnel. Sites will be instructed to submit this form to Syneos Health any time study drug is dispensed using these methods. The study monitor will arrange collection of unused study drug returned by the subject. All used and unused bottles will be returned to the sponsor. The study monitor will also perform an inventory of study drug at the close-out visit to the study center. All discrepancies must be accounted for and documented.

13.2 Financing and Insurance

Financing and insurance of this study will be outlined in a separate agreement between Syneos Health and the sponsor.

CONFIDENTIAL

14 ETHICS

14.1 Institutional Review Board

Before initiation of the study at each study center, the protocol, the ICF, other written material given to the subjects, and any other relevant study documentation will be submitted to the appropriate IRB. Written approval of the study and all relevant study information must be obtained before the study center can be initiated or the study drug is released to the investigator. Any necessary extensions or renewals of IRB approval must be obtained for changes to the study such as amendments to the protocol, the ICF or other study documentation. The written approval of the IRB together with the approved ICF must be filed in the study files.

The investigator will report promptly to the IRB any new information that may adversely affect the safety of the subjects or the conduct of the study. The investigator will submit written summaries of the study status to the IRB as required. On completion of the study, the IRB will be notified that the study has ended.

14.2 Regulatory Authorities

Relevant study documentation will be submitted to the regulatory authorities of the participating countries, according to local/national requirements, for review and approval before the beginning of the study. On completion of the study, the regulatory authorities will be notified that the study has ended.

14.3 Ethical Conduct of the Study

The investigators and all parties involved in this study should conduct the study in adherence to the ethical principles based on the Declaration of Helsinki, cGCP, ICH guidelines, and the applicable national and local laws and regulatory requirements.

14.4 Informed Consent

The process of obtaining informed consent must be in accordance with applicable regulatory requirement(s) and must adhere to cGCP.

The investigator is responsible for ensuring that no subject undergoes any study-related examination or activity before that subject has given written informed consent to participate in the study.

The investigator or designated personnel will inform the subject and their parent/legal representative of the objectives, methods, anticipated benefits and potential risks and inconveniences of the study. The subject and their parent/legal representative should be given every opportunity to ask for clarification of any points s/he does not understand and, if necessary, ask for more information. At the end of the interview, the subject and their parent/legal representative will be given ample time to consider the study. Subjects

CONFIDENTIAL

and their parent/legal representative will be required to sign and date the ICF/assent. There will be a separate ICF/assent for the PK part of the study. After signatures are obtained, the ICF/assent will be kept and archived by the investigator in the investigator's study file. A signed and dated copy of the ICF/assent will be provided to the subject and their parent/legal representative.

It should be emphasized that the subject may refuse to enter the study or to withdraw from the study at any time, without consequences for their further care or penalty or loss of benefits to which the subject is otherwise entitled. Subjects who refuse to give or who withdraw written informed consent should not be included or continue in the study.

If new information becomes available that may be relevant to the subject's willingness to continue participation in the study, a new ICF/assent will be approved by the IRBs (and regulatory authorities, if required). The study subjects and their parent/legal representative will be informed about this new information and reconsent will be obtained.

14.5 Subject Confidentiality

Monitors, auditors, and other authorized agents of the sponsor and/or its designee, the IRBs approving this research, and the United States FDA, as well as that of any other applicable agency(ies), will be granted direct access to the study subjects' original medical records for verification of clinical study procedures and/or data, without violating the confidentiality of the subjects to the extent permitted by the law and regulations. In any presentations of the results of this study or in publications, the subjects' identity will remain confidential.

All personal data collected and processed for the purposes of this study should be managed by the investigator and his/her staff with adequate precautions to ensure confidentiality of those data, and in accordance with the Health Insurance Portability and Accountability Act²⁰, applicable to national and/or local laws and regulations on personal data protection.

CONFIDENTIAL

15 REPORTING AND PUBLICATION, INCLUDING ARCHIVING

Essential documents are those documents that individually and collectively permit evaluation of the study and quality of the data produced. After completion of the study (end of study defined as the date of the last visit of the last subject), all documents and data relating to the study will be kept in an orderly manner by the investigator in a secure study file. This file will be available for inspection by the sponsor or its representatives. Essential documents should be retained for 2 years after the final marketing approval in an ICH region or for at least 2 years since the discontinuation of clinical development of the investigational product. It is the responsibility of the sponsor to inform the study center when these documents no longer need to be retained. The investigator must contact the sponsor before destroying any study-related documentation. In addition, all subject medical records and other source documentation will be kept for the maximum time permitted by the hospital, institution, or medical practice.

The sponsor must review and approve any results of the study or abstracts for professional meetings prepared by the investigator(s). Published data must not compromise the objectives of the study. Data from individual study centers in multicenter studies must not be published separately.

CONFIDENTIAL

17 APPENDICES

CONFIDENTIAL

17.1 Prohibited Medications

Drugs Allowed (Y) and Drugs Not Allowed (N) as Concomitant Medications			
Drug Class	Episodic Use (p.r.n)	Chronic Use	Restrictions
Analgesics	Y	Y	Non-narcotic analgesics only
Anesthetics General Local	N Y	N N	
Anorexics	N	N	
Antacids	Y	Y	
Antiacne	Y	Y	Topical agents only; Accutane (isotretinoin) is not allowed.
Antiangular Agents	N	N	
Antiarrhythmics	N	N	
Antibiotics	Y	(Call ^a)	Zyvox (linezolid) is prohibited
Anticoagulants	N	Y	Only aspirin (maximum 325 mg/day) is allowed as chronic anti-platelet treatment.
Anticonvulsants	N	N	
Antidepressants	N	N	
Antidiarrheal Preparations	Y	N	Only Imodium (loperamide hydrochloride), Pepto-Bismol, and kaolin preparations are allowed.
Antifungal Agents Systemic Topical	N Y	N Y	
Antihistamines	Y	(Call ^a)	Only Allegra (fexofenadine), Claritin (loratadine), Clarinex (desloratadine), and Zyrtec (cetirizine) are allowed. See Cough and Cold Preparations for combination products.
Antihypertensives	N	Y ^b	Diupres (reserpine), Catapres (clonidine), Minipress (prazosin), Inderal (propranolol), Wytensin (guanabenz), Tenex (guanafacine), and Aldomet (methyldopa) are not allowed.
Anti-impotence Medications	(Call ^a)	N	
Anti-inflammatory Drugs	Y	Y ^c	Indocin (indomethacin) and systemic corticosteroids are not allowed.
Migraine	(Call ^a)	N	Ergotamine or ergot derivatives are not allowed. Call ^a for use of triptans.
Antinauseants	Y	N	Only phosphoric acid preparations (Emetrol, Emecheck), Pepto-Bismol and cola syrup are allowed.

CONFIDENTIAL

Drugs Allowed (Y) and Drugs Not Allowed (N) as Concomitant Medications			
Drug Class	Episodic Use (p.r.n)	Chronic Use	Restrictions
Antineoplastics	N	N	
Antibesity	N	Y ^c	Only Xenical (orlistat) is allowed
Anti-Psoriatic Treatments	Y	Y	Soriatane (acitretin) is not allowed
Antipsychotics	N	N	
Antiviral Agents	Y	Y ^b	Only Zovirax, Valtrex, and Famvir are allowed
Anxiolytics	N	N	
Biotin	N	N	Biotin supplement > 2.5 mg total per day is not allowed. Biotin supplement ≤ 2.5 mg total per day is allowed.
Cough/Cold Preparations	Y	(Call ^a)	Use of cough and cold preparations containing pseudoephedrine are not permitted. Decongestants containing narcotics are not permitted. See Antihistamines.
Diuretics	Y	Y ^b	Episodic use of diuretics is restricted to treatment of premenstrual symptoms.
H ₂ Blockers/Proton pump inhibitors	Y	Y ^b	Tagamet (cimetidine) is not allowed.
Hormones	N	Y	Only thyroid hormone replacement, oral contraceptives, patch contraceptives, estrogen and progesterone replacement therapy are allowed. Hormone therapy (including oral contraceptives for female subjects) should not be initiated or discontinued within the 3 months prior to screening.
Hormone Suppressants	N	Y ^b	Only Proscar (finasteride) is allowed.
Hypoglycemic Agents	Y	Y	
Hypolipidemics	N	Y ^b	Only Mevacor (lovastatin), Zocor (simvastatin), Pravachol (pravastatin), Lipitor (atorvastatin), and Lescol (fluvastatin) are allowed.
Insulin	N	N	
Laxatives	Y	Y ^c	Only fiber-based products and Colace (docusate sodium) are allowed.
Muscle Relaxants	N	N	

CONFIDENTIAL

Drugs Allowed (Y) and Drugs Not Allowed (N) as Concomitant Medications			
Drug Class	Episodic Use (p.r.n)	Chronic Use	Restrictions
Psychotropic drugs not otherwise specified (including herbal products)	N	N	No drugs with psychomotor effects or with anxiolytic, stimulant, antipsychotic, or sedative properties are allowed.
Sedatives/Hypnotics	Y	N	Only Ambien (zolpidem) or Sonata (zaleplon) (no more than 3 times per week), at a maximum dose of 10 mg/day, is permitted if required for sleep.
Steroids - Systemic - Topical - Inhalant	N Y Y	N Y Y	
Vaccines	Y	N/A	

Abbreviations: N = No; N/A = not applicable; p.r.n. = pro re nata; Y = yes.

a Call the medical director to discuss.

b If being taken for at least 6 months before study and dose is stabilized.

c If being taken before admission to the study.

CONFIDENTIAL

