8. Female subjects who are not of childbearing potential do not need to use any methods of contraception. This includes preadolescent and adolescent females who have not reached menarche.

9. Female subjects who are sexually active and are of childbearing potential must use, with their partner, an approved method of highly effective contraception from the time of informed consent until 14 days after the last dose of study drug. In this patient population, a subject would be considered sexually active if they participate in any behaviors which may result in pregnancy. The following methods are acceptable:

- Combined (estrogen and progestogen containing) hormonal contraception associated with inhibition of ovulation and a barrier method (ie, condom for male partner):
 - oral

CONFIDENTIAL

- ii. intravaginal
- iii. transdermal

b. Progestogen-only hormonal contraception associated with inhibition of ovulation and a barrier method (ie, condom for male partner):

- i. oral
- ii. injectable
- iii. implantable intrauterine device
- iv. intrauterine hormone-releasing system

c. Surgical sterilization (vasectomy or bilateral tubal occlusion)

10. Strict abstinence is acceptable when it is in line with the subject's preferred and usual lifestyle. If a subject is usually not sexually active but becomes active, they, with their partner, must comply with the contraceptive requirements detailed above.

11. Female subjects of childbearing potential must have a negative serum beta-human chorionic gonadotropin pregnancy test at the Screening Visit, a negative urine pregnancy test at the Baseline Visit, and must not be breastfeeding.

12. Subject must have venous access sufficient to allow blood sampling and be compliant with blood draws as per the protocol.

13. Subject must be in general good health (defined as the absence of any clinically relevant abnormalities as determined by the investigator) based on screening physical and neurological examinations, vital signs, medical history, and clinical laboratory values (hematology, chemistry, and urinalysis). Note: If any of the hematology, chemistry, or urinalysis results are not within the laboratory's reference range, then the subject may be included only if the investigator determines the deviations to be not clinically relevant.

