14. Known hypersensitivity to escitalopram (escitalopram oxalate) or citalopram or any of the inactive ingredients, or had frequent or severe allergic reactions to multiple medications.
15. Have used escitalopram (at a minimum required dose and duration per FDA approval) and had a suboptimal effect as determined by the investigator.
16. Serious or unstable medical illness, or clinically significant laboratory or ECG result that, in the opinion of the investigator, would compromise participation in the study, confound results, or be likely to lead to hospitalization during the course of the study.
17. Hypo- or hyperthyroidism, unless stabilized on appropriate pharmacotherapy with no change in dosage for at least 3 months before the Screening Visit. If thyroid-stimulating hormone (TSH) is abnormal, the subject must have a normal triiodothyronine (T3) and thyroxine (T4).
18. Use of biotin as a dietary supplement at more than 2.5 mg total per day within 7 days of the Screening Visit.
19. Initiated or discontinued hormone therapy (including oral contraceptives for female subjects) within 3 months prior to screening.
20. Taking any medications that are contraindicated to escitalopram (escitalopram oxalate).
21. Inability to speak, read, or understand English well enough to complete the assessments.
22. Treatment with any investigational drug within 30 days or 5 half-lives (whichever is longer) prior to study entry.
23. Unlikely to comply with study requirements or unsuitable for any reason, including any indication the subject may be significantly impacted by the COVID-19 (or associated virus) pandemic, based on investigator judgement.
24. Employees or relatives of employees of investigational site, Syneos Health, or Allergan.
25. Family members or individuals living in the same household as the study subject.

CONFIDENTIAL

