8.3.5 Removal of Subjects From the Study

A subject may voluntarily withdraw or be withdrawn from the study at any time for reasons including, but not limited to, the following:

- Withdrawal of consent
- Use of non-permitted concurrent therapy
- Noncompliance with the study drug or study schedule
- Lost to follow-up
- Adverse event
- Investigator request
- Intercurrent illness
- Protocol deviation
- Pregnancy
- Sponsor request
- Lack of efficacy
- Due to the COVID-19 pandemic
- Death

Subjects who do not complete the study will not be replaced.

Subjects are free to withdraw from the study at any time without providing reason(s) for withdrawal and without prejudice to further treatment. The reason(s) for withdrawal will be documented in the electronic case report form (eCRF).

Subjects withdrawing from the study will be encouraged to complete the same final evaluations as subjects completing the study according to this protocol, particularly

CONFIDENTIAL

safety evaluations. The aim is to record data in the same way as for subjects who completed the study.

Subjects who withdraw early from the study should complete the End of Treatment Visit and enter the 1-week down taper period.

Subjects should be monitored for the following symptoms when discontinuing treatment: dysphoric mood, irritability, agitation, dizziness, sensory disturbances (eg, paresthesias such as electric shock sensations), anxiety, confusion, headache, lethargy, emotional lability, insomnia, and hypomania. A gradual reduction in dose rather than abrupt cessation is recommended, whenever possible.

Reasonable efforts will be made to contact subjects who are lost to follow-up (eg, 3 attempts to contact the subject by telephone/letter). These efforts must be documented in the subject's file.

The sponsor has the right to terminate the study at any time in case of serious adverse events (SAEs) or if special circumstances concerning the investigational product or the company itself occur, making further treatment of subjects impossible. In this event, the investigator(s) will be informed of the reason for study termination.

Pregnancy

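### Inclusion criterion 9 accepts four hormonal contraceptive routes that the closed list in Appendix 17.1 does not permit as concomitant medication; the two lists must be reconciled.

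*Protocol*

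**What the plan says.** **Entry criteria (protocol 8.3.2, criterion 9; same list in the synopsis).** "Female subjects who are sexually active and are of childbearing potential must use, with their partner, an approved method of highly effective contraception", and the duty runs "from the time of informed consent until 14 days after the last dose of study drug". The combined hormonal routes are oral, intravaginal ("ii. intravaginal") and transdermal. The second group is headed "Progestogen-only hormonal contraception associated with inhibition of ovulation and a barrier method (ie, condom for male partner"; its routes are oral, injectable ("ii. injectable"), an item printed as implantable intrauterine device, and an intrauterine hormone-releasing system. Surgical sterilization is the non-hormonal option. Criterion 10 accepts abstinence, and criterion 8 exempts girls not of childbearing potential.

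**Concomitant medication (Appendix 17.1, Hormones row).** Episodic use is marked no and chronic use yes, with the restriction "Only thyroid hormone replacement, oral contraceptives, patch contraceptives, estrogen and progesterone replacement therapy are allowed". A further sentence in the row concerns starting or stopping hormones before screening.

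**Related rules.** Exclusion criterion 19 reads "Initiated or discontinued hormone therapy (including oral contraceptives for female subjects) within 3 months prior to screening". Protocol 11.4.1.2 counts as concomitant any recorded medication used on or after the first dose. Protocol 8.3.5 lists "Use of non-permitted concurrent therapy" among the reasons a subject may be withdrawn and says that subjects who do not complete are not replaced. Protocol 11.2 and SAP 6.0 include concomitant medications among the categories of significant deviation to be summarized.

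**The concern.** The entry criteria and the concomitant-medication table both control hormonal contraception, and they do not control it in the same way. A girl established on an injection, an intravaginal method or a hormone-releasing intrauterine system passes the first and breaches the second.

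About 40 centers would each have to decide which text governs. One that follows the appendix may screen-fail a girl who meets the inclusion criterion, and the permitted reasons for re-screening in protocol 8.3.4 do not include this one. One that follows criterion 9 randomizes her, and she then carries a concomitant-medication deviation and a listed ground for withdrawal. A third course is to ask her to give up a method that the entry criteria accept. That touches subject safety as well as record-keeping, because pregnancy itself leads to withdrawal under protocol 8.3.5.

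A site looking for the answer is also misdirected: section 8.4.8.1 sends the reader to Appendix 17.2 for the prohibited-medication table, whereas the contents list shows 17.2 as the investigator signature page and 17.1 as the table.

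**Working it through.** The plan gives no figure on this point to reproduce. The check is a comparison of the two lists, a count, and a search for an exception.

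**Step 1. Each hormonal option in criterion 9 against the Hormones row**, reading transdermal as the patch:

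| Option printed in criterion 9 | On the Appendix 17.1 list? |
|---|---|
| Combined, oral | Yes |
| Combined, intravaginal | No |
| Combined, transdermal | Yes |
| Progestogen-only, oral | Yes |
| Progestogen-only, injectable | No |
| Progestogen-only, implantable intrauterine device (one item as printed) | No |
| Progestogen-only, intrauterine hormone-releasing system | No |

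**Step 2. Count.** Options: 3 combined + 4 progestogen-only = 7. On the list: 3. Not on the list: 7 − 3 = 4. If implantable and intrauterine device were meant as two items, the options are 8 and those not on the list 8 − 3 = 5. These are counts of methods, not of subjects.

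**Step 3. Does anything else reconcile the lists?**
- *Footnotes and discretion.* Other rows of Appendix 17.1 carry a call-the-medical-director entry or a footnote allowing stable prior use. The Hormones row has neither.
- *The replacement-therapy entry.* It is unlikely to cover these methods, because the row names contraceptives separately and by type.
- *Exclusion 19 and section 8.4.8.1.* Both restrict only starting or stopping hormones in the 3 months before screening. A stable user of an unlisted route passes both, so neither removes her before randomization.
- *Criterion 7.* It concerns male subjects. A partner's contraceptive is not the subject's concomitant medication, so it neither creates nor resolves the conflict.
- *Timing.* Criterion 9 runs from consent to 14 days after the last dose, and 11.4.1.2 counts any use on or after the first dose. The two rules therefore overlap for the whole treatment period.
- *Source.* The synopsis, section 8.3.2 and Appendix 17.1 are all current text; the conflict does not come from the amendment summary.

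No exception was found.

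**The case against.** The best case on the other side is that this is a clerical mismatch with little reach, and much of that stands.

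- *It does not affect every eligible girl.* A reader might infer that any girl meeting the entry criteria is in breach from Day 1. Criteria 8 to 10 do not support that: criterion 9 can be met by oral or transdermal methods or by sterilization, abstinence is accepted, and girls not of childbearing potential are exempt.
- *A stand-alone implant is not clearly listed.* The printed item is an implantable intrauterine device, so it cannot be asserted that a girl with a separate implant satisfies criterion 9.
- *No number of subjects can be given.* Neither document has data on contraceptive use, so any percentage of the 256 would be a guess.
- *Withdrawal is possible, not automatic.* Section 8.3.5 says a subject may be withdrawn. One who is withdrawn should still complete the End of Treatment visit, which includes the PARS (protocol 9.2.5), although under SAP 16.1 it counts as Week 8 only from Day 50.
- *The analysis is protected.* The mITT population has no exclusion for deviations, there is no per-protocol population, and the sample size already assumes 14% dropout. Significant deviations are to be reviewed before database lock.
- *The pregnancy risk is indirect.* A site that had a girl stop her method without substituting another accepted one, while she remained sexually active, would itself breach criterion 9.

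None of this removes the contradiction. Review before lock settles how a deviation is labelled after the event; it does not tell a site at screening which list to apply.

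**Conclusion.** The contradiction is real and sits in operative text. Criterion 9 accepts four of its seven printed hormonal options (five of eight on the alternative reading of one item) that the closed list in Appendix 17.1 does not permit. A girl who meets criterion 9 by one of those routes is on a non-permitted concomitant medication from her first dose.

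The conclusion rests on three readings: that the word Only makes the Hormones row a closed list, that transdermal means the patch, and that replacement therapy does not include contraception.

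The consequences are inconsistent screening, inconsistent deviation reporting, discretionary withdrawals without replacement, and the chance that a girl is asked to stop a method the entry criteria accept. How often this would occur cannot be determined from the documents. A reader might go on to infer a loss of power or a bias in the Week 8 comparison; the documents do not support that, since the sample size calculation and the primary model do not depend on either list. The point merits correction because it bears on subject safety and on uniform conduct across centers, and because it is cheap to correct. No position is taken on which methods should be allowed.

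**What to change.** 1. Reconcile criteria 9 and 10 (section 8.3.2 and the synopsis) with the Hormones row of Appendix 17.1, so that a single list governs both eligibility and concomitant use. The sponsor's medical lead decides its content.
2. In the same pass, clarify whether implantable intrauterine device is one item or two.
3. Before database lock, classify concomitant-medication deviations consistently with the reconciled list, including for subjects already randomized.
4. Correct the reference in section 8.4.8.1 from Appendix 17.2 to Appendix 17.1.

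The cost is an edit to a table row or to the criterion and its synopsis copy, plus one cross-reference, in the next amendment. It needs no new procedure and no change to the sample size or the analysis model.
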